1.3.7 Planned sample size

It is anticipated that a total of up to 55 subjects will be recruited. 15 subjects in Part A and 40 subjects in Part B. This is considered appropriate for an exploratory study and it is not based on formal statistical sample size calculation. In the event subjects do not complete treatment due to any reasons other than exceedance of organ dose limits or treatment-related safety issues, additional subjects will be recruited as replacements to ensure an adequate sample size in the “per protocol set” for safety evaluation. Subjects with non-interpretable dosimetry scans may be replaced upon agreement of the investigator and the sponsor.

For Cohorts 3 and 6 in Part B, to detect a difference between two peptide doses within the same cohort, the total sample size of eight is calculated. Assuming 30% standard deviation of the paired difference, there is 80% power to detect a 2-fold-change, and 99% power to detect a 3-fold change at a 2-sided alpha of 0.05.

2 SUBJECT ANALYSIS SETS

The following Analysis Sets will be used during statistical analyses

Screened Subjects Set, i.e. all subjects screened (i.e. who signed the informed consent)

Eligible Subjects Set, all subjects who comply with the inclusion and exclusion criteria (according to the investigator/site) and have entered the study (performed the Screening Visit).

2.1 Efficacy

2.1.1 Intent-To-Treat Set (ITT)

The Intent-to-Treat Set (ITT) consists of all subjects in the Eligible Subjects Set who received study medication.

2.1.2 Per Protocol Set (PP)

The Per-Protocol Set (PP) consists of all subjects in the ITT Set who complete the study according to the protocol with no major protocol deviation. Any protocol deviation will be evaluated by the Sponsor based on the individual case. Major protocol deviations will be defined in the Protocol Deviations Document and identified in a data review meeting before database lock.

2.2 Safety

The Safety Analysis Set (SAS) will consist of all subjects who received study medication.

2.3 Dosimetry

2.3.1 Intent-To-Treat Dosimetry Analysis Set (ITT-DAS)

The Intent-To-Treat Dosimetry Analysis Set (ITT-DAS) consists of all subjects in the ITT Set for whom at least one complete set of dosimetry imaging and dosimetry blood sample measurements is available.

2.3.2 Per Protocol Dosimetry Analysis Set (PP-DAS)

The Per Protocol Dosimetry Analysis Set (PP-DAS) will consist of all subjects in the ITT-DAS for whom no major protocol violations occurred affecting dosimetry variables.

2.4 Pharmacokinetics

2.4.1 Radiopharmaceutical Pharmacokinetic Set

For Part A and Part B, the Radiopharmaceutical Pharmacokinetic Set will consist of all subjects in the ITT Set who receive at least one dose of study medication and have at least one measured radioactive concentration in blood.

2.4.2 OPS201 Pharmacokinetic Set (Part B only)

For Part B only, the OPS201 Pharmacokinetic Set will consist of all patients in the ITT Set who receive at least one dose of study medication and have no major protocol deviations affecting the PK variables and who have a sufficient number of OPS201 levels to estimate the main PK parameters (i.e. C_{max} , T_{max} , and Area Under the Curve (AUC)).

2.4.2.1 OPS201 Pharmacokinetic Set in Plasma (Part B only)

For Part B only, the OPS201 Pharmacokinetic Set will consist of all patients in the ITT Set who receive at least one dose of study medication and have no major protocol deviations affecting the plasma PK variables and who have a sufficient number of plasma OPS201 levels to estimate the main PK parameters (i.e. C_{max} , T_{max} , and Area Under the Curve (AUC)).

2.4.2.2 OPS201 Pharmacokinetic Set in Urine (Part B only)

For Part B only, the OPS201 Pharmacokinetic Set will consist of all patients in the ITT Set who receive at least one dose of study medication and have no major protocol deviations affecting the urine PK variables and who have all urine OPS201 levels available to estimate the main urine PK parameters (i.e. A_e , f_e and Cl_R).

2.5 Primary Analysis Set

The primary analysis based on the assessment of the safety and tolerability of the study drug (primary objective) will be performed on the Safety Analysis Set (SAS).

The efficacy analysis will be performed on the ITT and PP sets.

Patients will be assigned to each analysis set prior to the statistical analysis.

3 STATISTICAL METHODS

3.1 Statistical analysis strategy

The statistical analyses will be performed in accordance with ICH E9 guideline [3] and will be based on the pooled data from the individual study sites, unless otherwise stated. Statistical analyses will be performed by Covance.

3.1.1 Primary safety endpoint(s)

Frequencies and/or descriptive summaries of standard safety and tolerability parameters: AEs (including SAEs) according to National Cancer Institute (NCI) Common Terminology Criteria for Adverse Events (CTCAE) v5.0 and vital signs, laboratory tests (haematology, biochemistry and urinalysis, and pituitary markers), 12-lead and Holter electrocardiogram (ECG), DLTs, physical examination results and use of concomitant medication throughout the study.

3.1.2 Secondary endpoint(s)

3.1.2.1 Biodistribution and Radioactive Pharmacokinetics of the Radiopharmaceutical Endpoints

Biodistribution and Pharmacokinetics (including radioactive decay) of the Radiopharmaceutical endpoints are:

(a) Maximal uptake (unit: %) in lesions.

The maximal uptake in lesions will be calculated for each lesion as:

$$\text{Maximal uptake (\%)} = \frac{\text{Maximal activity (Bq)}}{\text{Injected activity (Bq)}} \times 100$$

With:

Maximal activity (unit: Bq): the maximal activity in each eligible lesion, on all the assessment performed within each cycle (at Visits 1-3: 4 hours, 24 hours, 48 hours, 72-96 hours, and 144-168 hours post infusion).

Injected radioactivity (IA) (unit: Bq): the actual radioactivity administered/injected.

Maximal uptake (%) in lesions will be computed for each administration of ¹⁷⁷Lu-OPS201 (visits 1, 2, 3, 4 and 5). Uptake (%) at each time point will be also calculated and displayed for the statistical analysis.

(b) Maximal uptake (unit: %) in discernible organs.

The maximal uptake in discernible organs will be calculated with the same formula as for the lesions.

Discernible organs will be identified during the course of the study.

Maximal uptake (%) in discernible organs will be computed for each administration of ¹⁷⁷Lu-OPS201 (visits 1, 2, 3, 4 and 5). Uptake (%) at each time point will be also calculated and displayed for the statistical analysis.

(c) Area Under the Curve (AUC) of ¹⁷⁷Lu-OPS201 in discernible thoracic and abdominal organs (unit: MBq*h), lesions (unit: MBq*h) and blood (unit: MBq/L*h).

The AUCs of ¹⁷⁷Lu-OPS201 will be computed through sum of exponential functions fitting and integration (Ref. 11) as described in the Dosimetry Calculation Procedure Manual.

AUC of ¹⁷⁷Lu-OPS201 radioactivity in discernible thoracic and abdominal organs, lesions and blood will be computed for each administration of ¹⁷⁷Lu-OPS201.

Radioactivity uptake in blood in percentage of the IA per liter (unit: %/L) at each assessment time point will be also displayed (i.e. at Visit 1: before infusion, at stop of infusion (0), 5 minutes ± 1 minute, 30 minutes ± 3 minutes, 1 hour ± 5 minutes, 4 hours ± 10 minutes, 24 ± 1 hours, 48 ± 1 hours and 72-96 hours and 144-168 hours after the stop of infusion, Visits 2, 3, 4 and 5: before infusion, at stop of infusion (0), 1 hour ± 5 minutes, 4 hours ± 10 minutes, 24 ± 1 hour, 48 ± 1 hour, 72-96 hours and 144-168 hours).

(d) Terminal half-life of radioactivity concentrations in blood (unit: h).

The terminal half-life is defined as the lowest decay rate of the AUC fit performed for blood (Ref. 11).

- (e) Other biodistribution and radioactive pharmacokinetics of the radiopharmaceutical variables

Cumulatively excreted activity in urine (unit: MBq) in each time period, 0 to 6 hours and 6 to 24 hours post-infusion (Part A), and 0 to 4 hours, 4 to 24 hours, 24 to 48 hours (Part B).

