3.2.2 Secondary Endpoints and Evaluations

3.2.2.1 Biodistribution and Radioactive Pharmacokinetics of the Radiopharmaceutical Endpoints

- Maximal uptake (%) at the target lesions;
- Maximal uptake (%) in discernible organs and blood;
- AUC of ^{177}Lu -OPS201 in discernible thoracic and abdominal organs, target lesions and blood;
- Terminal half-life of radioactivity concentrations of the radiopharmaceutical in blood.

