AUCs of ^{177}Lu -OPS201 in discernible thoracic and abdominal organs (unit: h*MBq) will be listed by study part, cohort (part B only), radioactivity level adapted or not (part B only), subject, cycle and organ. Descriptive statistics, including geometric mean and geometric Coefficient of Variation (CV), will be presented by study part, cohort (part B only), cycle, organ on the PP-DAS.

AUCs of ^{177}Lu -OPS201 in lesions (unit: h*MBq) will be listed by study part, cohort (part B only), radioactivity level adapted or not (part B only), subject, cycle and lesion number.

AUCs of ^{177}Lu -OPS201 in blood (unit: MBq/L*h) will be listed by study part, cohort (part B only), radioactivity level adapted or not (part B only), subject and cycle. Descriptive statistics, including geometric mean and geometric Coefficient of Variation (CV), will be presented by study part, cohort (part B only) and cycle on the Radiopharmaceutical Pharmacokinetic Set.

- Uptake in blood (unit: %/L)

At each assessment time point will also displayed, it will be listed by study part, cohort (part B only), radioactivity level adapted or not (part B only), subject, cycle and time point. Descriptive statistics, including geometric mean and geometric Coefficient of Variation (CV), will be presented by study part, cohort (part B only), cycle and time point on the Radiopharmaceutical Pharmacokinetic Set. Graphs of the mean of the uptake in blood (unit: %/L) over time will be displayed by study part, cohort (part B only), radioactivity level adapted or not (part B only) and cycle on the Radiopharmaceutical Pharmacokinetic Set.

- Terminal half-life of radioactivity concentrations of the radiopharmaceutical in blood (unit: h).

Terminal half-life of radioactivity concentrations in blood (unit: h) will be listed by study part, cohort (part B only), radioactivity level adapted or not (part B only), subject and cycle. Descriptive statistics, including geometric mean and geometric Coefficient of Variation (CV), will be presented by study part, cohort (part B only), radioactivity level adapted or not (part B only) and cycle on the Radiopharmaceutical Pharmacokinetic Set.

- Cumulatively excreted radioactivity in urine (unit: MBq) in each time period, 0 - 6 hours, 6 - 24 hours and 24 - 48 hours and overall on the 0-48 hours period (if there is no missing collection period).

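### SAP 3.1.2.1(d) defines the terminal half-life in blood as a decay rate, so the stated rule gives a value in 1/h under a label of hours

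*SAP*

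**What the plan says.** Protocol 3.2.2.1 names the secondary endpoint, "Terminal half-life of radioactivity concentrations of the radiopharmaceutical in blood", without a formula. Protocol 11.4.4 leaves further description of the biodistribution parameters to the SAP.

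SAP 3.1.2.1 supplies that description:

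- Its opening line makes clear that physical decay is not removed: "Pharmacokinetics (including radioactive decay) of the Radiopharmaceutical endpoints are" the items that follow.
- Item (c) says that the AUCs "will be computed through sum of exponential functions fitting and integration (Ref. 11) as described in the Dosimetry Calculation Procedure Manual". The blood AUC is in megabecquerels per litre times hours: "lesions (unit: MBq*h) and blood (unit: MBq/L*h").
- Item (d) is headed "Terminal half-life of radioactivity concentrations in blood (unit: h") and then gives the rule: "The terminal half-life is defined as the lowest decay rate of the AUC fit performed for blood". The sentence closes with a citation of Ref. 11, the paper on the fitting software.

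SAP 3.2.2(a) says "Terminal half-life of radioactivity concentrations in blood (unit: h) will be listed by study part", cohort, subject and cycle. It adds descriptive statistics with geometric mean and geometric CV. It repeats the unit and gives no conversion. The visible items of SAP 7.1 (Appendix 1, derived data) contain none either.

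**The concern.** The heading and the definition under it describe two different quantities. A half-life is a time; a decay rate is the reciprocal of a time. They also move in opposite directions: the longer activity stays in the blood, the larger the half-life and the smaller the rate.

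This is the only derivation rule that the documents give for a named secondary endpoint, so a programmer working from the SAP alone has nothing else to follow. According to Protocol 11.4.6 and SAP 3.1, dosimetry is assessed at a central site and the statistical analysis is done by a separate contractor. A sentence that calls a rate a half-life leaves it unclear which of the two is to be transferred and tabulated.

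**Working it through.** The documents state no value for the blood half-life, so there is no figure to reproduce. The check is one of dimension and direction.

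**Inputs**

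- Model: sum of exponentials (SAP 3.1.2.1(c)), C(t) = Σ Aᵢ · exp(−λᵢ t).
- Time unit: hours, from the unit of the blood AUC. Each λᵢ is therefore in 1/h.
- Decay: included (opening line of SAP 3.1.2.1), so each λᵢ is an effective rate.
- Physical half-life of ¹⁷⁷Lu: 6.65 days (Protocol 1.2) = 6.65 × 24 = 159.6 h.
- Half-lives of 40, 60 and 80 h: assumed for illustration, not in the documents.

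**Step 1: what the rule returns.** At late times the term with the smallest rate dominates, so λ_min is the correct terminal phase. The terminal half-life is t½ = ln 2 / λ_min, in hours. The rule as written stops at λ_min, in 1/h.

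**Step 2: numbers.** λ_min = ln 2 / t½:

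| Half-life (h) | Value the literal rule would list |
|---|---|
| 40 (assumed) | 0.6931 / 40 = 0.0173 |
| 60 (assumed) | 0.6931 / 60 = 0.0116 |
| 80 (assumed) | 0.6931 / 80 = 0.0087 |
| 159.6 (physical decay only) | 0.6931 / 159.6 = 0.0043 |

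The order is reversed: the subject at 80 h gets half the value of the subject at 40 h.

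**Step 3: which summaries could be repaired.** Take three subjects at the assumed 40, 60 and 80 h.

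- Arithmetic mean: the true mean is 60.0 h. The mean rate is (0.01733 + 0.01155 + 0.00866) / 3 = 0.01251 per h, and ln 2 divided by it is 55.4 h. The true mean is not recovered.
- Geometric mean: (40 × 60 × 80)^(1/3) = 57.7 h. ln 2 divided by the geometric mean rate is also 57.7 h. It is recovered exactly.
- Geometric CV: it depends only on the SD of the logs. Since ln t½ = ln(ln 2) − ln λ, that SD is the same for both, here 0.348. It is unaffected.
- Minimum and maximum, which SAP 3.2.15 also plans: the smallest rate belongs to the longest half-life, so the two exchange places.

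Individual listed values could each be converted and the tables rerun. The loss concerns anyone who has only the summary tables.

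**The case against.** The strongest reply is that the sentence is a loose summary and not the working procedure. It cites Ref. 11, and item (c) sends the reader to the Dosimetry Calculation Procedure Manual; neither was available to this review. SAP 3.2.13 says that Appendix 1 holds only some of the derivations, and part of that appendix is redacted. The heading, and the analysis section with "Terminal half-life of radioactivity concentrations in blood (unit: h) will be listed", show that hours are meant. Any half-life above 0.69 h gives a literal value below 1, so a column of such values headed in hours would look odd to most reviewers.

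All of that stands, and it limits the point. It does not make the sentence correct: the SAP states a rule, and the rule gives the wrong quantity.

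Three stronger readings are tempting, and the documents do not support them.

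- A reader might infer that every reported half-life will be wrong. That follows only if the sentence is programmed literally, which the documents do not show.
- A reader might divide the half-life by the literal value and quote an error factor in the thousands. For pure physical decay, 159.6 / 0.00434 is about 36,750, but the unit is h². In days the same division is 6.65 / 0.1042, or about 64. A ratio that changes with the time unit is not an error size.
- A reader might infer that a comparison of blood retention across peptide masses would point the wrong way. Tables by cohort and cycle permit an informal look in Cohorts 3 and 6, but no comparison of blood half-life is planned. SAP 3.1.9 rules out formal testing. The between-visit ratios in SAP 3.2.2(b) concern specific absorbed dose and the tumour-to-kidney ratio. The board's decision table in SAP 3.2.19 turns on dose-limiting toxicities, receptor saturation and mass-dose or receptor modelling, and the accompanying rules use marrow and kidney absorbed dose. None of them names blood half-life.

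**Conclusion.** The definition is wrong as written, and the point is minor. Under the stated rule the endpoint is a rate in 1/h with its ordering reversed. Arithmetic means in the summary tables could not be converted back, while the geometric mean could be and the geometric CV would not change.

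This rests on two readings of SAP 3.1.2.1: that the fit runs in hours, and that decay is left in. It describes what the text prescribes, not what the program does. The endpoint is secondary and descriptive, its intended unit is stated beside the faulty sentence, and nothing visible ties it to a dose decision.

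**What to change.** In SAP 3.1.2.1(d), replace the sentence with: *The terminal half-life (h) is ln 2 divided by the lowest decay rate (1/h) of the sum-of-exponentials fit to the blood time-activity curve (effective half-life, including radioactive decay).*

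Then confirm that the programmed derivation and the Dosimetry Calculation Procedure Manual use the same formula, and that the variable passed to the statistical contractor is the half-life and not the rate.

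The cost is one SAP sentence and one program check. No data collection, analysis set or clinical rule changes.

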3.1.3 Radiation dosimetry endpoint(s)

Radiation dosimetry endpoints are the following (calculations methods are described in the Dosimetry Calculation Procedure Manual):

- (a) Absorbed dose in organs/ lesion (unit: Gy).

- (b) Specific absorbed dose to the lesions (unit: Gy/GBq)

The specific absorbed dose to the lesions is the absorbed dose by the lesion (unit: Gy) divided by the injected radioactivity (unit: GBq) for each lesion selected for dosimetry evaluation.

Specific absorbed dose to the lesions (unit: Gy/GBq) will be computed for each administration of ^{177}Lu -OPS201 (visits 1, 2 and 3) on part A, and on Part B (Cohort 1, 3 and 6), for each lesion lesion evaluable in dosimetry (all lesion and by lesion location) when at least 3 patients in the same cohort is having a lesion in the same organ, by visit and overall.

- (c) Specific absorbed dose per organ (unit: Gy/GBq).

The specific absorbed dose for a given organ is the absorbed dose by this organ (unit: Gy) divided by the injected radioactivity (unit: GBq).

Specific absorbed dose per organ (unit: Gy/GBq) will be computed for each administration of ^{177}Lu -OPS201 (visits 1, 2 and 3) and any additional cycle.

- (d) Cumulative absorbed doses in organs and lesions selected for dosimetry evaluation (unit: Gy).

The cumulative absorbed organ dose is calculated as the sum of the absorbed dose over all the ^{177}Lu -OPS201 administration cycles. In case absorbed dose is missing for at least one of the ^{177}Lu -OPS201 administration cycles, cumulative absorbed dose is extrapolated from available data at the other cycles by dosimetry expert.

Cumulative absorbed doses will be provided per organ and for lesions selected for dosimetry evaluation.

CCI

3.1.5 OPS201 Pharmacokinetics (Part B only)

In subjects in plasma OPS201 PK Set, plasma PK parameters of OPS201 (including, but not limited to, maximum observed concentration (C_{\max}), AUC, elimination half-life ($t_{1/2}$), apparent total body clearance of the drug from plasma (CL), apparent volume of distribution (Vd)) will be derived using the non-compartmental approach on the individual plasma concentration-time profiles of OPS201.

In subjects in urine OPS201 PK Set, urine PK parameters of OPS201 (including, but not limited to, cumulative amount of unchanged drug excreted into the urine (Ae), renal clearance of the drug from plasma (CLR)) will be derived using the non-compartmental approach.

Derivation and analysis of PK data will be documented in a separate Data Analysis Plan.

3.1.6 Secondary Efficacy Endpoints

The efficacy endpoints are:

- (a) Objective tumour response based on RECIST v1.1 (CT/MRI scan)
- Best overall response (BOR)

The best overall response according to RECIST v1.1 is defined as the best response recorded from the initiation of treatment until the EOCT/ EOAC/EW Visit, prior to the assessment of PD. Confirmation of complete or partial response is not required.

The following table provides a summary of the overall response status calculation at each time point for subjects who have measurable disease at baseline:

Table 4 Time point response

Target Lesions	Non-Target Lesions	New Lesions[a]	Time Point Response (TPR)
CR	CR	No	CR
CR	NCRNPD	No	PR
CR	NE	No	PR[b]
CR	NA[c]	No	CR
PR	NE	No	PR[b]
PR	CR	No	PR
PR	NCRNPD	No	PR
PR	NA[c]	No	PR
SD	NE	No	SD
SD	CR	No	SD
SD	NCRNPD	No	SD
SD	NA[c]	No	SD
NE	Non-PD	No	NE
PD	ANY	Yes/No	PD
ANY	PD	Yes/No	PD
ANY	ANY	Yes	PD

CR: Complete Response, PR: Partial Response, SD: Stable Disease, PD: Progressive Disease, NE: Not Evaluable, NCRNPD: Non-CR/Non-PD, NA: Not Applicable.

- a Identification of new lesions at a post-Screening time point will result in a TPR of PD. If an identified new lesion subsequently becomes NE, the TPR will be recorded as PD unless the new lesion has proven to have resolved. Note: TPRs assessed after a progression event will not contribute to the determination of the Best Response.
- b If a non-target lesion is classified as NE, a designation of PR may be assigned based on information from the target lesions.
- c No non-target lesions identified at Screening.

When SD or Non CR/Non Progressive Disease is believed to be the best overall response, it needs to be assessed a minimum of 8 weeks [56 days] after start of treatment. Otherwise, the best overall response will be NE, unless any Progressive Disease was further documented, in which case BOR will be Progressive Disease.

- Overall Response Rate (ORR)

The Overall Response Rate (ORR) is defined as the proportion of participants who achieved a Complete Response (CR) or a Partial Response (PR) as best overall response according to RECIST v1.1 criteria in the ITT Set. Subjects with no tumour assessment after the start of study treatment will not be evaluated.

- Disease Control Rate (DCR)

The DCR is defined as the proportion of participants who achieved a Complete Response (CR), a Partial Response (PR) or a Stable Disease (SD) as best overall response according to RECIST v1.1 criteria in the ITT Set. Subjects with no tumour assessment after the start of study treatment will be considered as with no disease control.

- Sum of diameters as percentage change

- Percentage change from baseline in the target lesions identified in the RECIST v1.1 assessment and/or the initial lesion(s) identified at eligibility as being >20 mm in diameter, calculated as:

$$\text{Percentage change from baseline} = \frac{(D_i - D_0)}{D_0} \times 100$$

With

D_i the sum of the longest diameters of the target lesions as per RECIST v1.1 at the time point/Visit i .

D_0 the sum of the longest diameters of the target lesions as per RECIST v1.1 at baseline.

- Best percentage change from baseline in sum of target lesions longest diameters, calculated as:

$$\text{Best percentage change from baseline} = \frac{(D_{min} - D_0)}{D_0} \times 100$$

With:

D_{min} the minimum sum of the longest diameters as per RECIST v1.1 on all measurement time points.

D_0 the sum of the longest diameters of the target lesions as per RECIST v1.1 at baseline.

Correlations will be computed between dosimetry parameters (cumulative absorbed dose) and volume and diameter changes in lesions at the last visit of the core trial (EOCT or EACT or EW as applicable).

(b) Progression Free Survival (PFS)

PFS will be evaluated up to two years after the EOCT/EOAC Visit and will be based on RECIST v1.1 status assessed by investigator assessment. PFS will be assessed by independent central review up to EOCT/EOAC/EW Visit (during the core study part).

PFS is defined as the time from start of study treatment until occurrence of tumour progression or death.

(c) Quality of life using EORTC QLQ C30 v3.0 and QLQ GLNET21 (2006) questionnaires.

- EORTC QLQ C30 v3.0

The European Organisation for Research and Treatment of Cancer (EORTC) score questionnaire (QLQ-C30) will be used for quality of life (QoL) evaluation.

Following the EORTC recommendations, fifteen scales can be derived from the initial 30 questions:

- A global health status/QoL scale,
- Five functional scales (physical, role, cognitive, emotional and social),
- Nine “symptoms” scales /items (nausea and vomiting, pain, fatigue, dyspnoea, insomnia, appetite loss, constipation, diarrhoea and financial difficulties).

Of note, for functional scales, a higher value reflects a better level of function, but for symptoms scales /items a higher value reflects worse symptoms; moreover high score for the global health status represents a high QoL.

Each scale in the questionnaire will be scored (0 to 100) according to the EORTC recommendations in the EORTC QLQ-C30 Scoring Manual. The scoring method is summarized below. In this summary, Q_i refers to the i^{th} question on the EORTC QLQ-C30.

Table 5 Scoring and scale dimension for EORTC QLQ-C30:

	Number of items (range[a])	Item number
Global health status / QoL		
Global health status/QoL	2 (6)	29,30
Functional scales		
Physical functioning	5 (3)	1 to 5
Role functioning	2 (3)	6, 7
Emotional functioning	4 (3)	21 to 24
Cognitive functioning	2 (3)	20, 25
Social functioning	2 (3)	26, 27
Symptom scales / items		
Fatigue	3 (3)	10, 12, 18
Nausea and vomiting	2 (3)	14, 15
Pain	2 (3)	9, 19
Dyspnoea	1 (3)	8
Insomnia	1 (3)	11
Appetite loss	1 (3)	13
Constipation	1 (3)	16
Diarrhoea	1 (3)	17
Financial difficulties	1 (3)	28

[a] Item range is the difference between the possible maximum and the minimum response to individual items; most items take values from 1 to 4, giving range = 3.

For all scales, the RawScore, RS, is the mean of the component items:

$$\text{RawScore RS} = (I_1 + I_2 + \dots + I_n) / n$$

Then **for Functional scales:**

$$\text{Score} = \left\{ 1 - \frac{(RS - 1)}{\text{range}} \right\} \times 100$$

and for **Symptom scales / items** and **Global health status / QoL:**

$$\text{Score} = \left\{ \frac{(RS - 1)}{\text{range}} \right\} \times 100$$

Missing value (item) consideration for scoring:

The scale scores will only be calculated if at least half of the items from the scale have been answered. Otherwise, no score will be calculated, and the scale score will be set to missing.

For single-item measures, the score will be missing if the question is not answered.

- EORTC QLQ – GI.NET21 (2006)

The GI.NET21 module is intended for use among subjects with gastrointestinal related (GI.-related) neuroendocrine tumours, who vary in disease stage and treatments.

The module comprises 21 questions, consisting of 5 scales and 4 single items, assessing disease symptoms, side effects of treatment, body image, disease related worries, social functioning, communication and sexuality. The module has been developed according to the EORTC guidelines. The GI.NET21 has been translated into several European languages.

Each question is quoted from 1 (Not at all) to 4 (very much). The scoring algorithm for the scales and single items is described below:

Table 6 Scoring and scale dimension EORTC QLQ – GI.NET21:

	Number of items (range[a])	Item number
Scales		
Endocrine symptoms scale	3 (3)	31, 32, 33
G.I. symptoms scale	5 (3)	34 to 38
Treatment related symptom scale	3 (3)	39, 40, 46
Social function scale	3 (3)	42, 44, 49
Disease related worries scale	3 (3)	41, 43, 47
Single items		
Muscle /bone pain symptom	1 (3)	48
Sexual function	1 (3)	51
Information/communication function	1 (3)	50
Body Image	1 (3)	45

[a] Item range is the difference between the possible maximum and the minimum response to individual items; most items take values from 1 to 4, giving range = 3.

For all scales, a high score is equivalent to worse or more problems.

For all scales, the RawScore, RS, is the mean of the component items:

$$RawScore RS = (I_1 + I_2 + \dots + I_n) / n$$

Then for each of the five **scales** and for each **single item**:

$$Score = \left\{ \frac{(RS - 1)}{range} \right\} \times 100$$

Missing value (item) considerations for scoring are the same as for the QLQ-C30 questionnaire presented above.

